### 10.1.2 Supporting Analysis: Time-normalized Number of HAE Attacks in Treatment Period 1 and 2 (Open-label Part)

In addition to the primary analysis, the time-normalized number of HAE attacks per month will also be summarized descriptively for the [REDACTED] mg and [REDACTED] mg CSL312 q4wk regimens for the following:

- Treatment Period 2 evaluation period (alone).
- Treatment Period 1 and Treatment Period 2 evaluation periods (combined) for subjects who received the same dose continuously during both treatment periods (data will only be included until the date of the planned dose reduction following Amendment 2 in Treatment Period 2).

The time-normalized number of HAE attacks per month will also be summarized descriptively for the [REDACTED] mg CSL312 q2wk regimen for subjects with C1-INH HAE for the efficacy evaluation period of Treatment Period 1 and for the [REDACTED] mg CSL312 q4wk regimen for subjects with FXII/PLG HAE for the efficacy evaluation periods of Treatment Period 1, Treatment

Period 2, and combined Treatment Period 1 and Treatment Period 2 (only applicable for subjects with FXII/PLG HAE).

The efficacy evaluation periods are defined in Section 8.2.8.

There will be no testing of the of [CCI] mg CSL312 q2wk dose against placebo q4wk or the [CCI] mg CSL312 q4wk dose against placebo q4wk for subjects with FXII/PLG HAE.

Subjects profiles will be generated for each subject. Subjects will be grouped by treatment sequence as for the by-subject listings as described in Section 7. The x-axis will show the Run-in Period, Treatment Period 1 and Treatment Period 2. The different subject IDs will be plotted on the y-axis. [CCI]

[REDACTED]

[REDACTED]

[REDACTED]

[REDACTED]

[REDACTED]

Subject profiles will be reviewed to detect possible patterns of missing values due to drop-outs, e.g., due to many attacks.

### 10.1.3 [CCI]

[CCI]

[REDACTED]

CCI [Redacted]

10.1.4 CCI [Redacted]

CCI [Redacted]

10.1.5 CCI [Redacted]

CCI [Redacted]

## 10.2 Secondary Efficacy

Secondary efficacy endpoints will be analyzed for Treatment Period 1 and Treatment Period 2 separately. In addition, both treatment periods will be analyzed together for subjects who received the same dose continuously during both treatment periods (data will only be included until the date of the planned dose reduction following Amendment 2 in Treatment Period 2). The evaluation periods are defined in Section 8.2.8.

### 10.2.1 Analysis of Responders

A subject is classified as a responder if the percentage reduction in time-normalized number of HAE attacks per month is  $\geq 50\%$  as compared to the Run-in Period. The percentage reduction is calculated within a subject as:

$$100 * [1 - (\text{TNA CSL312} / \text{TNA Run-in})]$$

where TNA CSL312 is the time-normalized number of HAE attacks per month during treatment with CSL312 and TNA Run-in is the time-normalized number of HAE attacks per month during the Run-in Period.

The number and percentage of subjects classified as responders and non-responders will be presented along with 95% CI.

CCI

In Treatment Period 2, the comparison between CCI mg and CCI mg CSL312 q4wk will only include data collected prior to the planned dose reduction following Amendment 2.

A by-subject listing will be provided as specified in Section 7 with the response classification and the degree of reduction in time-normalized number of HAE attacks per month.

### 10.2.2 Analysis of Attack-free Subjects

The number and percentage of subjects who do not experience a HAE attack will be presented.

CCI

### 10.2.3 Analysis of HAE Attacks

The number and percentage of mild, moderate, and severe HAE attacks will be presented as well as the time-normalized number of mild, moderate, and severe HAE attacks per month. The number and percentage of subjects experiencing at least 1 mild, moderate, or severe HAE attack will also be presented.

The severity of HAE attacks will be included in the by-subject listing (see Section 10.1).

#### **10.2.4 Analysis of HAE Attacks Treated With On-demand HAE Medication**

A treated HAE attack is defined as a HAE attack which started during the corresponding evaluation period for Treatment Period 1 or 2 and during which (start and end date including) on-demand medication to treat HAE attacks was taken (i.e., has been started).

The number and percentage and the time-normalized number of treated and untreated HAE attacks per month overall and by severity will be presented. A summary table will be provided with

- Number and percentage of subjects with at least 1 treated HAE attack;
- Number and percentage of subjects with only treated HAE attacks;
- Number and percentage of subjects with HAE attacks but without treated attacks;
- Number and percentage of subjects with no attacks at all (attack-free subjects);
- Descriptive statistics for the number and percentage of treated attacks per subject.

This analysis will be repeated for moderate or severe HAE attacks only.

A by-subject listing will be provided as specified in Section 7 and with the additional information of type of on-demand HAE medication (Berinert, Firazyr, Ruconest, Kalbitor, Cinryze, or Other), start date and time of the on-demand HAE medication, dose (unit), route, frequency, the date and dose of the last and next CSL312 (or placebo) administration, HAE attack identifier, start and end date and time of the HAE attack, location(s), and severity.

#### **10.2.5 PK Analysis of CSL312 in Subjects With C1-INH**

Please refer to Section 12.

#### **10.2.6 Analysis of Safety and Tolerability of CSL312 in Subjects With C1-INH**

Please refer to Sections 11.3, 11.4, 11.5, 11.6, 11.7, 11.8.

### 10.3 CCI

CCI

#### 10.3.1 CCI

CCI

#### 10.3.2 **Analyses of Time-normalized Uses of On-demand HAE Medication per Month**

Only for subjects with C1-INH HAE, the time-normalized number of uses of on-demand HAE medication per month will be summarized descriptively.

On the “Acute HAE Treatment” eCRF page, it will be entered if on-demand treatment for a HAE attack is needed and if so, what medication was used (Berinert, Firazyr, Ruconest, Kalbitor, Cinryze, or Other), the dose, route, and frequency administered, and the start date and time as well as the HAE attack identifier.

On-demand medications for treatment of a HAE attack during the efficacy evaluation period which will be administered during a HAE attack, will be included in the calculation of the time-normalized number of uses of on-demand medication for the treatment of a HAE attack. The start date and time of the administration of the on-demand medications will be compared with the start and end dates of the HAE attacks described in Section 10.1. Only if the date of an administration of an on-demand medication is between the start (including) and end date (including) of a HAE attack, the on-demand medication will be included in the calculation of the time-normalized number of uses of on-demand HAE medication per month.

The time-normalized number of uses of on-demand HAE medication per month will be calculated as:

$$\frac{\text{(number of uses of on-demand HAE medication / length of subject's evaluation period)}}{30.4375} *$$

where the length of subject's evaluation period is defined in Section 8.2.8.

CCI [Redacted]

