Primary Endpoint The primary endpoint is the time-normalized number of HAE attacks.

Secondary Objective(s) The secondary objectives of the study are:

1. To further evaluate the efficacy of CSL312 in subjects with C1-INH HAE.
2. To evaluate the PK of CSL312 in subjects with C1-INH HAE.
3. To evaluate the safety and tolerability of CSL312 in subjects with C1-INH HAE.

Secondary Endpoint(s) The secondary endpoints of the study are:

1. Responder subjects.
2. HAE attack-free subjects.
3. HAE attacks.
4. HAE attacks treated with on-demand HAE medication.
5. CSL312 PK in plasma:
 - Maximum concentration (C_{max}).
 - Area under the concentration-time curve in 1 dosing interval ($AUC_{0-\tau}$).
 - Time of maximum concentration (T_{max}).
 - Terminal elimination half-life ($T_{1/2}$).
 - Total systemic clearance (CL_{tot}).
 - Volume of distribution during the elimination phase (V_z).
6. Subjects experiencing the following safety events:
 - Adverse events.
 - Serious adverse events.
 - Adverse events of special interest (ie, anaphylaxis, thromboembolic events, and bleeding events).
 - Injection site reactions.

- Inhibitory antibodies to CSL312.
 - Clinically significant abnormalities in laboratory assessment that are reported as adverse events.
-

- Number of Subjects** Up to 50 subjects are planned to be assigned to treatment with investigational product in Treatment Period 1, including:
- 8 subjects with C1-INH HAE who will be assigned to receive placebo q4wk.
 - 8 subjects with C1-INH HAE who will be assigned to receive [redacted] mg CSL312 q4wk.
 - 8 subjects with C1-INH HAE who will be assigned to receive [redacted] mg CSL312 q4wk.
 - 8 subjects with C1-INH HAE who will be assigned to receive [redacted] mg CSL312 q4wk.
 - Up to 8 subjects with C1-INH HAE who will be assigned to receive [redacted] mg CSL312 q2wk.
 - Up to 10 subjects with FXII/PLG HAE who will be assigned to receive [redacted] mg CSL312 q4wk.
-

- Study Duration** The duration of the study for an individual subject who participates in Treatment Period 1 and Treatment Period 2 is up to approximately 83 weeks if the duration of Treatment Period 2 is not extended. This estimation is based on:
- A Screening Period of up to 4 weeks.
 - A Run-in Period of up to 8 weeks.
 - A treatment period of ~13 weeks (Treatment Period 1).
 - A treatment period of ~44 weeks (Treatment Period 2).
 - A Follow-up Period of ~14 weeks.

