The number, the time-normalized number, and the percentage of treated and untreated attacks overall and by severity will be presented by treatment. The above will also be presented as rate per month. A treated HAE attack will be defined as a treatment-emergent HAE attack during which on-demand medication to treat HAE attacks was taken. The number and percentage of subjects with at least 1 treated attack, the number and percentage of subjects with only treated attacks, the number and percentage of subjects with attacks but without treated attacks, and the number and percentage of subjects with no attacks at all will be presented by treatment. These analyses will be repeated including moderate or severe attacks only. The above will also be presented as rate per month.

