### 8.1.2 Imputation of Partial Dates

If the start or end date of an event is missing, then the duration of the event will naturally also be missing.

There will be no imputation of partially or completely missing dates. See Section [11.2](#) for the handling of partially or completely missing AE start dates. See Section [0](#) for the handling of partially or completely missing start and end dates of concomitant medication.

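### On-demand doses are tied to attacks by calendar date although the eCRF records which attack each dose was for, so treated attacks can be misclassified

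*SAP*

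**What the plan says.** The protocol synopsis and Table 2 list "HAE attacks treated with on-demand HAE medication" as a secondary endpoint for Treatment Period 1. Protocol 10.3.2.2 gives the definition: "A treated HAE attack will be defined as a treatment-emergent HAE attack during which on-demand medication to treat HAE attacks was taken".

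SAP 10.2.4 turns this into a date rule. The attack must start in the evaluation period and be one "during which (start and end date including) on-demand medication to treat HAE attacks was taken". The attack identifier appears in that section only as a column of the by-subject listing.

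SAP 10.3.2 covers on-demand uses per month, a descriptive endpoint outside the secondary list. It says that the Acute HAE Treatment eCRF page holds the medication, "the dose, route, and frequency administered, and the start date and time as well as the HAE attack identifier". It then derives the count without that identifier: "The start date and time of the administration of the on-demand medications will be compared with the start and end dates of the HAE attacks". A use counts "Only if the date of an administration of an on-demand medication is between the start (including) and end date (including) of a HAE attack".

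On incomplete dates, SAP 8.1.2 states: "There will be no imputation of partially or completely missing dates". It refers the reader elsewhere for adverse events and concomitant medication, but gives no rule for HAE attacks.

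**The concern.** The investigator records directly which attack each dose was for. The SAP reconstructs that link from calendar days and describes no check of one against the other. The reconstruction can go wrong in three ways:

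- **Shared date.** One attack ends and another starts on the same day. One dose that day falls within the inclusive dates of both, so both become treated.
- **Dose dated outside its attack.** A dose carrying an attack's identifier but dated before its onset or after its end is not counted. The attack is then called untreated unless another dose falls within its dates.
- **No end date.** The test of lying between start and end cannot be applied, and no imputation is allowed. The classification is undefined.

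At stake is the number and share of treated and untreated attacks, overall and by severity, which SAP 4.6.1 also schedules for each interim analysis. The 10.2.4 listing will show identifier and dates side by side. Table and listing can therefore disagree, with no rule on which one governs.

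**Working it through.** The plan states no misclassification or agreement rate, so there is no figure to reproduce. The check has two parts.

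**Reading the rules against each other.** Suppose attack A ends on the morning of a given day, attack B starts that evening, and one dose is taken that evening with B's identifier. By identifier, B is treated and A is not. By clock time, the dose was not taken during A either. By the inclusive dates of SAP 10.2.4, both are treated. Clock times for attacks exist, since the SAP 10.1 listing shows start and end date and time for each attack identifier, but 10.3.2 compares the dose with attack dates. The number of uses is one under either rule, because the dose lies within an attack in both cases.

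**Size of the shared-date effect.** Inputs from the documents:

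- attack rates of 0.6 (CSL312) and 2.9 (placebo) per month, SAP 4.5;
- 8 subjects per arm, SAP 4.5;
- evaluation from Day 6 to Day 91, SAP 8.2.8, so 91 − 6 = 85 days (the SAP's extra day in the duration is immaterial here);
- a month of 30.4375 days, SAP 8.2.3.

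Expected attacks per arm = rate × 85 / 30.4375 × 8:

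- CSL312: 0.6 × 85 / 30.4375 × 8 = 13.4
- placebo: 2.9 × 85 / 30.4375 × 8 = 64.8

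The rest is assumed, because the documents do not give it: attacks arise at random and do not overlap in clock time; durations are exponential with mean 0.5, 1 or 2 days; 50% or 80% of attacks are treated; each treated attack gets one dose, within 12 hours of onset and before the attack ends. In 4,000 simulated subjects per setting, the same attacks were classified by identifier and then by inclusive dates.

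About 2% of attacks share a date with another attack at 0.6 per month (1.7 to 2.3%), and about 9% at 2.9 per month (8.7 to 9.2%). The date rule raises the treated share as follows (percentage points, from unrounded values):

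| Mean duration (days) | Treated (assumed) | At 0.6/month | At 2.9/month |
|---|---|---|---|
| 0.5 | 50% | 0.3 | 1.5 |
| 0.5 | 80% | 0.2 | 0.9 |
| 1 | 50% | 0.2 | 1.1 |
| 1 | 80% | 0.2 | 0.8 |
| 2 | 50% | 0.1 | 1.0 |
| 2 | 80% | 0.1 | 0.6 |

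For example, with a mean of 0.5 days and 50% treated at 2.9 per month, the treated share is 50.3% by identifier and 51.8% by date.

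In attacks per arm, this is at most 13.4 × 0.003 = 0.04 for CSL312 and 64.8 × 0.015 = 0.97 for placebo. With the same duration and treated proportion in both arms, the distortion of the between-arm difference runs from 0.6 − 0.1 = 0.5 to 1.5 − 0.3 = 1.2 points.

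The count of uses was identical under both rules in every setting. Doses dated outside their attack and missing end dates were not simulated, since nothing in the documents suggests how often they occur.

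**The case against.** The strongest reply is that the SAP simply applies the protocol's definition, which asks for medication taken during the attack. A rule based on the identifier alone would count doses dated outside it. Protocol 13.5.2 already provides for consistency checks and queries, the 10.2.4 listing makes disagreements visible, and SAP 8.2 leaves full derivations to dataset specifications that are not public. The analyses as described are descriptive, and the shared-date effect is small.

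Much of this stands. The effect is small, and the documents show only that misclassification can happen. The point about the protocol's wording is fair for doses dated outside the attack, and it is why such cases should be listed and queried. It does not defend the shared-date case, where inclusive dates are looser than the protocol's definition. General data checks, a listing and unseen specifications do not alter the derivation rule written in the SAP.

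A reader might also infer more than the documents support:

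- **A shift of about 7 points in an active arm.** One misclassified attack among 13.4 is 1 / 13.4 = 7.5%. That is the leverage of a single hypothetical attack and not an expected error.
- **Attacks without an end date count as untreated.** The SAP does not say so; it leaves them unclassified. For the Treatment Period 1 endpoint, attacks still open at an interim cut are also few: the first interim follows completion of that period by the blinded subjects and the second by the open-label subjects, so only attacks spanning its end are concerned.
- **Missing end dates bias the arms differently.** Fewer attacks give each one more weight, but that is not bias. Nothing suggests that end dates are missing more often per attack in one arm.
- **Uses per month is a secondary endpoint distorted in the same way.** It is outside the secondary list, and shared dates do not change it.

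**Conclusion.** The point holds as a modest defect in a stated rule. SAP 10.2.4 and 10.3.2 infer a link that the eCRF records directly, and the inferred rule has one case that gives a wrong answer (shared dates), one that drops recorded doses (dates outside the attack) and one with no answer (missing end date). Treated attacks, a secondary endpoint, can therefore be misclassified.

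The part that can be sized is about 0.1 to 0.3 percentage points in the treated share at 0.6 attacks per month and 0.6 to 1.5 at 2.9 per month. This rests on the planning rates and on the assumed durations, treated proportions and dosing pattern; at an assumed 6 attacks per month it would be about 1 to 3 points. The other two cases have no documented frequency. Uses per month can change only through those two. The primary endpoint and its Mann-Whitney tests count attacks and not treatments, so they are untouched. This is a cheap improvement and not a threat to the trial's conclusions.

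**What to change.** In SAP 10.2.4, define a treated attack as one that starts in the evaluation period and has at least one on-demand administration carrying its HAE attack identifier. In SAP 10.3.2, count uses by the same link.

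Use overlap of date and time, rather than of date alone, only where the identifier is missing. State how an attack is classified when both the identifier and the end date are missing. List every case where identifier and dates disagree, and query it before each Data Review Meeting; this keeps the result in line with the protocol's requirement that medication be taken during the attack.

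The cost is a change of SAP wording and a merge on a field already collected, with no new data. The downside is reliance on the investigator's recorded link and a small amount of query work.

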10.3.3 CCI [Redacted]

CCI [Redacted]

CCI [Redacted]

- CCI [Redacted];
- CCI [Redacted];
- CCI [Redacted];
- CCI [Redacted];
- CCI [Redacted];
- CCI [Redacted];
- CCI [Redacted];
- CCI [Redacted];
- CCI [Redacted]

CCI [Redacted]

10.3.4 CCI [Redacted]

CCI [Redacted]

### 10.3.5 CCI [REDACTED]

CCI [REDACTED]

## 10.4 Treatment Compliance

Compliance will be summarized for the ITT population for the SC injections in each treatment period and both periods together for subjects who received the same dose continuously during both treatment periods (data will only be included until the date of the planned dose reduction following Amendment 2 in Treatment Period 2). The IV infusions will not be included in the compliance analysis. The administered volume of each injection will be taken from the data base. The study medication has a concentration of CCI mg per mL. To maintain the blind, the doses in the blinded part of Treatment Period 1 will be volume-normalized. It is planned that all SC injections will contain mL. If in the blinded study part, the subject is randomized to CCI mg CSL312, the mL injection will contain purely the study medication. For the CCI mg and the CCI mg CSL312 group, the study

medication will be diluted in a [REDACTED] and [REDACTED] ratio, respectively. For the derivation of the actual dose, it is assumed that the dilution will take place as planned. For the open-label part, the study medication is not diluted.

From the actual volume of an injection as in the database and considering the randomized dose, the actual dose will be derived as:

$$\text{Actual dose (mg)} = (\text{actual volume [mL]} / K [\text{mL/mg}]) * 100,$$

where  $K =$  [REDACTED] or [REDACTED] mL/mg for [REDACTED] mg, [REDACTED] mg, or [REDACTED] mg CSL312 q4wk in the blinded arm and [REDACTED] for the open-label arms.

Compliance for dose (mg) will be calculated as

$$\text{Compliance (\%)} = [\text{total cumulative actual dose} / \text{total planned dose}] * 100,$$

where the total planned dose will be derived from the subject's exposure and planned treatment schedule (q2wk or q4wk) as

$$(\text{duration of exposure in days} / (7 * X)) * \text{planned dose} + \text{planned dose}$$

where (duration of exposure in days) is rounded down to the nearest integer which can be divided by 7 and  $X = 2$  or  $4$  corresponds to q2wk or q4wk, respectively.

Only the administered doses will be considered for the total cumulative actual dose which are identical to the planned treatment. The planned treatment is the randomized treatment in Treatment Period 1 and in Treatment Period 2 prior to the planned dose reduction following Amendment 2. For C1-INH HAE subjects randomized to [REDACTED] mg CSL312 in Treatment Period 2, the planned treatment after dose reduction changes to [REDACTED] mg CSL312. Exposure duration will depend on the treatment period and subject's course of the study. Definitions are provided in Section 8.2.8.

The following summaries will be provided:

- Descriptive statistics for compliance (%) over the entire treatment period, for Treatment Period 1 plus the first three doses of Treatment Period 2 (administration on site), and for Treatment Period 2 after the first three doses (administration at home);
- Number and percentage of subjects in the compliance categories < 80%, 80 – 120%, and > 120% and < 90%, 90 - 110%, and > 110% for the periods specified above.

A by-subject listing as specified in Section 7 and with the following additional information will be provided:

- Randomized, planned and actual treatments;

- Compliance in Treatment Period 1 plus the first three doses of Treatment Period 2, after the first three doses in Treatment Period 2, and over the entire study.

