- ^h The test for beta-human chorionic gonadotropin will be performed for women of childbearing potential (only). A serum or urine pregnancy test may be used. A serum pregnancy test will be performed by the site if urine result is inconclusive.
- ⁱ Subjects may use the on-demand medication of their choice to treat HAE attacks experienced during the study if that medication has previously been shown to be effective (see [Section 7.2](#)).
- ^j Investigational product will be administered IV by the investigator or delegate at the study site during the Week 1 (Day 1) Visit, and will be self-administered SC by the subject under supervision of the investigator or delegate at the study site during the Week 1 (Day 6) Visit, the Week 5 (Day 35) Visit, and the Week 9 (Day 63) Visit.
- ^k For subjects who do not participate in Treatment Period 2, the final dose of investigational product will be administered at the Week 9 (Day 63) Visit.
- ^l The Treatment Period 1 Follow-up Visit may be waived in place of a telephone contact. If the Treatment Period 1 Follow-up is conducted as a visit, then a blood draw for assessment of PK / [REDACTED] should occur.

Abbreviations: CCI [REDACTED]; CCI [REDACTED]; C1-INH HAE = hereditary angioedema with C1-esterase inhibitor deficiency; C4 = complement C4; eDiary = electronic diary; HAE = hereditary angioedema; CCI [REDACTED]; IRT = interactive responses technology; CCI [REDACTED]; PK = pharmacokinetic; SC = subcutaneous; CCI [REDACTED]; [REDACTED]; CCI [REDACTED].

Footnotes to the Schedule of Assessments: Treatment Period 1 [C1-INH HAE Subjects Receiving Investigational Product Every 2 Weeks]

- ^a For subjects who are taking part in Treatment Period 2, the Week 13 (Day 85) Visit is the first study visit in Treatment Period 2; refer to the [Schedule of Events: Treatment Period 2 \[All Subjects\]](#). If a subject is discontinued from the study before completing Treatment Period 1, the subject will undergo the assessments scheduled for the Week 13 (Day 85) Visit and then attend the Treatment Period 1 Follow-up Visit ~14 weeks later.
- ^b If a subject participates in Treatment Period 2, then the subject will not attend the Treatment Period 1 Follow-up Visit. Refer to the [Schedule of Events: Treatment Period 2 \[All Subjects\]](#) for the visit schedule for subjects who participate in Treatment Period 2.
- ^c The Week 10 (Day 64) Visit is optional, and blood for assessment of PK / [REDACTED] may be collected off-site.

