#### *Subjects with C1-INH HAE*

The first 32 eligible subjects with C1-INH HAE will be randomly assigned to receive treatment (■ mg CSL312 q4wk; ■ mg CSL312 q4wk; ■ mg CSL312 q4wk; placebo q4wk) with investigational product in a ratio of 1:1:1:1 during Treatment Period 1 as described in detail in Section 4.4. Subjects will receive a single intravenous (IV) loading dose of investigational product followed by three subcutaneous (SC) doses, depending on the randomized treatment arm in the following way:

- A single loading dose of ■ mg CSL312 IV followed by ■ mg CSL312 administered every 4 weeks (q4wk) (SC).
- A single loading dose of ■ mg CSL312 IV followed by ■ mg CSL312 q4wk SC.
- A single loading dose of ■ mg CSL312 IV followed by ■ mg CSL312 q4wk SC.

- A single loading dose of placebo IV followed by placebo q4wk SC.

For these first 32 subjects with C1-INH HAE, Treatment Period 1 will be conducted in a blinded manner, and the investigational product will be volume-normalized to maintain the blind.

After the first 32 subjects with C1-INH HAE are randomly assigned to study treatment, up to an additional 8 subjects with C1-INH HAE will be assigned to receive [REDACTED] mg CSL312 administered every 2 weeks (q2wk). [REDACTED]. For these C1-INH HAE subjects, Treatment Period 1 will be conducted in an open-label manner and the investigational product will not be volume-normalized.

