**Treatment Period 1 (subjects who participate in Treatment Period 2):**

Week 13 Day 85/91 Visit date and time – 1 – date and time of first administration of study treatment + 1.

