**Treatment Period 1 (subjects who do NOT participate in Treatment Period 2):**

Study Completion Visit date and time – date and time of first administration of study treatment + 1.

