## 9.2 Protocol Violations

Protocol violations are those protocol deviations which may identify subjects who should be excluded from one or more analysis population(s). Listings showing subjects with protocol deviations will be generated prior to each interim and the final analysis to identify subjects who may have these protocol violations. During the Data Review Meetings, the subject assignment to analysis populations will be discussed in detail based on the consolidated protocol deviations from the █ along with the listings of the potential protocol violations specified below. It cannot be ruled out that during the discussion of protocol deviations, additional violations which are not listed below will be considered to

have a significant impact and will thus lead to exclusion of subjects from analysis population(s). The decisions made during the Data Review Meetings will be documented in detail in the Data Review Meeting minutes and may modify the specifications in the list below. The Data Review Meeting minutes will be agreed upon prior to each interim and final analysis.

Potential Protocol Violations	Potential Exclusion From Analysis Population
Subject did not provide informed consent (informed consent date missing)	Screening, Safety, ITT, PP, PK, (b) (4)
Subject randomized but not treated with study treatment	Safety, PP, PK, (b) (4)
Subjects treated with incorrect study treatment	PP, potentially PK, (b) (4)
Subject randomized and treated but does not have at least one measurable PK concentration	PK
Subject randomized and treated but does not have at least one (b) (4) measurement	(b) (4)
Subject randomized and treated but without primary efficacy assessment	PP
Subject randomized and treated but violated inclusion or exclusion criteria	PP, potentially also PK, (b) (4)
Subject randomized and treated but compliance outside 80-120%	PP, potentially also PK, (b) (4)
Subject randomized and treated but received prohibited concomitant medication	PP, potentially also PK, (b) (4)

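### The compliance formula in SAP 10.4 plans at least one SC dose too many, so a fully adherent CSL312 q4wk subject scores 75% or less in Treatment Period 1

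*SAP*

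**What the plan says.** SAP 10.4 defines compliance as cumulative actual SC dose over total planned dose, times 100. Total planned dose is "duration of exposure in days} / (7 * X)) * \text{planned dose} + \text{planned dose", where exposure days are first rounded down to a multiple of 7 and X is 2 (q2wk) or 4 (q4wk). The loading dose does not count: "The IV infusions will not be included in the compliance analysis".

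SAP 10.4 takes the exposure duration from SAP 8.2.8. For Treatment Period 1 (TP1) there are two cases:

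- Subjects entering Treatment Period 2 (TP2): "Week 13 Day 85/91 Visit date and time – 1 – date and time of first administration of study treatment + 1".
- Subjects not entering TP2: "Study Completion Visit date and time – date and time of first administration of study treatment + 1".

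The number of q4wk doses is fixed elsewhere. SAP 4.1.2 describes a "loading dose of investigational product followed by three subcutaneous (SC) doses". Footnote j of the protocol's q4wk TP1 schedule places the SC doses "during the Week 1 (Day 6) Visit, the Week 5 (Day 35) Visit, and the Week 9 (Day 63) Visit". The protocol's List of Conventions makes the Day 91 dose the first dose of TP2.

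Two outputs use the result. SAP 10.4 tabulates "Number and percentage of subjects in the compliance categories < 80" per cent, 80-120% and above 120% (with a second set of cut-offs at 90% and 110%). SAP 9.2 lists "Subject randomized and treated but compliance outside 80-120" per cent as a potential reason for exclusion from the per-protocol (PP) population, and possibly from the PK population.

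**The concern.** Adding one dose to (days / interval) is right when the time span runs from the first dose to the last, because n doses enclose n − 1 intervals. The spans in SAP 8.2.8 do not end at the last dose. They run on through a full final dosing interval to the next visit, so that interval already accounts for the last dose and the extra term counts a dose nobody is scheduled to receive.

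If so, the compliance tables understate adherence throughout. In q4wk TP1, where only three doses are due, one phantom dose is enough to push full adherence below the 80% limit. That covers the three blinded CSL312 arms (24 of the 32 blinded subjects) and the FXII/PLG subjects on the same schedule. A PP rule tied to that limit would then flag subjects who missed nothing.

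**Working it through.** The documents give no worked compliance value. The figure to reproduce is the scheduled dose count: 3 for q4wk TP1.

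**Inputs**

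- Planned doses = floor7(exposure days)/(7X) + 1, where floor7 rounds down to a multiple of 7. The quotient itself is not rounded (SAP 10.4).
- q4wk TP1 SC doses: Days 6, 35, 63, so 3 (SAP 4.1.2; protocol footnote j).
- q2wk TP1 SC doses: Days 1, 15, 29, 43, 57, 71, so 6 (Protocol 8.5.3).
- TP2 doses: Day 91, then every 28 days to Day 371, so 11 before the Day 399 visit (Protocol 3.2.2).
- First administration: Day 1 (the IV dose for q4wk).

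**Main case: q4wk, entering TP2**

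Exposure = 91 − 1 − 1 + 1 = 90 days; floor7 = 84. Planned = 84/28 + 1 = 4. Compliance with all three doses given = 3/4 = 75.0%.

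**Other completed periods, full adherence, nominal days**

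| Period | Exposure days | floor7 | Planned | Scheduled | Score |
|---|---|---|---|---|---|
| q4wk TP1, entering TP2 | 90 | 84 | 4 | 3 | 75.0% |
| q4wk TP1, not entering TP2 | 91 | 91 | 4.25 | 3 | 70.6% |
| q2wk TP1, entering TP2 | 84 | 84 | 7 | 6 | 85.7% |
| TP2, Day 91 to 399 | 309 | 308 | 12 | 11 | 91.7% |
| TP2, Day 85 to 399 | 315 | 315 | 12.25 | 11 | 89.8% |
| TP1 and TP2, same dose | 399 | 399 | 15.25 | 14 | 91.8% |

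**Could another duration in SAP 8.2.8 be meant?** For q4wk TP1 the adverse-event period from Day 6 is 91 − 1 − 6 + 1 = 85 days and the efficacy period is 91 − 6 + 1 = 86 days. Both floor to 84 and again plan 4 doses. The formula returns 3 if the span is Day 6 to Day 63 (58 days, floor7 = 56, 56/28 + 1 = 3), but SAP 8.2.8 defines no such span.

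**Timing of the Week 13 visit** (q4wk, entering TP2; the TP1 visit window is not legible in the available text, so this range is an assumption): Days 80-84 give 3/3.75 = 80.0%, Days 85-91 give 75.0%, Days 92-98 give 3/4.25 = 70.6%.

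**TP1 plus the first three TP2 doses**, a span that SAP 10.4 also reports without giving an end day. If it ends on Day 147: 147/28 + 1 = 6.25, and 6/6.25 = 96.0%. If it ends on Day 174: floor7 = 168, 168/28 + 1 = 7, and 6/7 = 85.7%. Both end days are assumptions.

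**q4wk subjects who stop early in TP1 having received every dose due** (exposure = stopping day)

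| Stop | floor7 | Planned | Given | Score |
|---|---|---|---|---|
| Day 34 | 28 | 2 | 1 | 50.0% |
| Day 40 | 35 | 2.25 | 2 | 88.9% |
| Day 50 | 49 | 2.75 | 2 | 72.7% |
| Day 62 | 56 | 3 | 2 | 66.7% |
| Day 66 | 63 | 3.25 | 3 | 92.3% |

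All five are fully adherent; the score depends only on the day of stopping.

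**The case against.** The arithmetic is not in dispute; the case against concerns its cause and its weight.

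- **The extra dose is not the only fault.** A fully dosed subject who stops exactly on a dosing day still falls short: 2/2.25 = 88.9% on Day 35 and 3/3.25 = 92.3% on Day 63. Exposure starts at the excluded IV dose and the quotient is not cut to whole doses. That produces the additional quarter dose in the 70.6% and 91.8% cases. For subjects starting TP2 on Day 85, the first interval of 119 − 85 = 34 days has the same effect. This stands, and it is a reason to replace the formula rather than trim it.
- **Only q4wk TP1 taken alone crosses 80% among completed periods.** The others score 85.7% to 91.8%. The by-subject listing in SAP 10.4 has no TP1-only column. True, but SAP 10.4 also asks for compliance in each treatment period, so the TP1 summary remains, and subjects who stop after TP1 have no later doses to dilute the error.
- **No exclusion is automatic.** SAP 9.2 calls these potential violations and lets the Data Review Meeting modify the list. TP1 doses are supervised on site and recorded in the eCRF, so the meeting could see that all three were given. This stands and limits the damage. It also means case-by-case decisions to override a pre-specified rule because its formula is wrong.
- **PP is secondary.** SAP 10.1 uses ITT for the primary analysis. This stands.

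**Conclusion.** The formula is wrong as written. On nominal days it plans 4 SC doses in q4wk TP1 for subjects entering TP2, and 4.25 for those who stop after TP1, against 3 scheduled. Full adherence therefore scores 75.0% or 70.6% and falls in the lowest compliance category. The error recurs in q2wk TP1 (7 planned against 6) and TP2 to Week 57 (12 against 11), without crossing the 80% limit.

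The PP consequence is conditional. If TP1 compliance feeds the SAP 9.2 criterion, or a subject ends after TP1, fully adherent CSL312 q4wk subjects are flagged. If combined or whole-study compliance is used for subjects who continue to Week 57, they score about 92% and are not. The primary ITT result does not change. The correction should be made, but it does not threaten the trial's main conclusion.

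The figures assume nominal visit days and TP2 not extended beyond Week 57. They cover the CSL312 arms only, because how the mg-based formula applies to placebo cannot be read from the visible text.

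**What to change.** In SAP 10.4, define total planned dose as the planned dose multiplied by the number of SC administrations scheduled before the end of the period or the subject's discontinuation. On the documents' own schedules that is 3 for q4wk TP1, 6 for q2wk TP1 and 11 for TP2 to Week 57 if not extended. Every case in the tables above then scores 100%.

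Deleting the added dose is not enough. With exposure as SAP 8.2.8 defines it, fully dosed q4wk subjects stopping on Days 40, 50, 66 and 70 would have 35/28, 49/28, 63/28 and 70/28 planned doses and score 160%, 114%, 133% and 120%. Starting exposure at the first SC dose as well changes these to 160%, 133%, 150% and 133%.

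Two clarifications belong with the change. State in SAP 9.2 which period's compliance governs PP membership; TP1 is the natural choice for a TP1 endpoint, though this is a separate decision from the arithmetic. State in SAP 10.4 how compliance is derived for placebo.

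The cost is a short edit to SAP 10.4, one sentence in SAP 9.2 and reprogramming of one derived variable.
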